1.1 STUDY OBJECTIVES

1.1.1 PRIMARY OBJECTIVE

The primary objective of this study is to collect descriptive data to support feasibility, acceptability, safety, and potential for effectiveness.

- The potential for effectiveness is determined by examining participants' pre-test and post-test scores for SI and depression.
- The study will also collect data to guide refinements to the product and the workflow for product use.
- Participants will complete 12 sessions over approximately 12 weeks.
- Participants will complete assessments at baseline and weeks 1, 4, 8, and 12.
- Acceptability is determined from rates of session completion, rolling retention rate (percentage of participants who use the app on or after a set timeframe), and the system usability scale (SUS; Bangor et al., 2008), which indicates the extent to which participants found Oui's app usable.
- We will also conduct semi-structured user-feedback interviews.

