Given the variable nature of symptomatology associated with suicide risk, particularly SI, a reasonable marker of lower suicide risk following treatment is a reduction in suicide attempts during the follow-up period (Stanley et al 2018). Two CBT interventions have been proven to be efficacious in helping prevent reattempts at suicide: Brief CBT (BCBT; [name] et al 2015) and Cognitive Therapy for Suicide Prevention (CT-SP, Brown et al 2005). **BCBT** is 12- sessions and is also implemented in three phases. Phase 1 consists of assessment, cognitive behavioral conceptualization, crisis response planning (CRP), and basic emotion-regulation skills. Phase 2 emphasizes cognitive strategies to reduce vulnerability to suicidal behaviors. Phase 3 focuses on relapse prevention. [name] et al.'s (2015) RCT recruited individuals with a suicide attempt or clear SI and showed a 60% reduction in suicide attempts relative to controls at 18-months. **CT-SP** has been developed using a 10-session protocol consisting of three phases: early (engagement, risk assessment, safety planning, means restriction), intermediate (cognitive restructuring and coping skills training) and later (relapse prevention). Brown et al.'s (2005) RCT recruited individuals following a suicide attempt and showed a 50% reduction in suicide attempts relative to controls at 18 months. Two recent trials testing elements of BCBT and CT-SP, the Attempted Suicide Short Intervention Protocol (Gysin-Maillart et al 2016), and CRP ([name] et al 2017) provided even more support for psychological treatments that directly target two key mechanisms contributing to suicidality: emotion regulation and cognitive flexibility. Additionally, CRP was associated with significantly faster decline in SI as measured by the Beck Scale for Suicide Ideation (BSS; Beck et al 1991). Recently, Sinyor et al. (2020) examined BCBT in youth hospitalized after an episode of suicidal behavior and despite small numbers, found a significant reduction in suicide behavior in the BCBT group. In light of these collective findings, several procedures pulled from BCBT and CT-SP have been recommended for standard care with suicidal patients by the National Alliance for Suicide Prevention (2018). However, despite existence of these interventions, some shown to be efficacious nearly 15 years ago (Brown et al 2005), and recommendations by experts, neither are widely integrated into standard care for suicidal patients (Ghahramanlou-Holloway et al 2014).

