
summary reports, overseeing recruitment and enrollment and the execution of other research related tasks at IOL. Since this IRB approval will only cover the feasibility open trial, Drs. [name] and [name] are the only investigative team members listed as study personnel on the IRB application. For the feasibility open trial, Oui will not have direct contact with participants. Oui will provide technical support if needed, communicated by way of IRB-approved study staff at the ADC. Coded data from the feasibility open trial will be shared with Oui through a secure data transfer system (e.g., REDCap or password protected file sent via secure e-mail). In order to download the app, the participant will need to register directly with Oui. No PHI is required for app registration and download. The only data collected directly through the app is number of log ins and number of treatment modules completed. Oui's data and security for user information is detailed in the Data Security and Resource Sharing Plan section below. Oui has also signed a Business Associate Agreement with HHC (see attached).

INNOVATION

Several aspects of this application are novel. First, in the wake of the FDA's new guidance (2017) on mobile applications, this project attempts to capitalize on this guidance to address a great unmet need (reduction of youth suicide attempts). We are not aware of any other mobile technology attempting to address this issue in this way for youth. Second, the proposed project will lay the groundwork for a large, randomized clinical trial (RCT) powered to detect differences in rates of suicide attempts among youth recently discharged from a psychiatric hospital. Whereas most clinical trials in depression and related disorders are powered to detect differences in symptom severity or SI as measured by clinical rating scales, the next line of research following the successful completion of this project would use suicide attempts as a primary outcome. Third, the current project will involve feedback from multiple stakeholders, including patients, providers, administrators, and third-party payers. By considering the needs and perspectives of these various stakeholders, such an approach greatly enhances the likelihood that a clinically successful intervention will be adopted into clinical practice. Some additional innovative aspects of this project are outlined below.

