
MILESTONE 1. Completion of Alpha [REDACTED] Review within 30 days.

B.1.2. Beta Version Development. Beta Version Development for this project will be orchestrated by the Oui development team (including four team members identified as Other Personnel in the Budget Justification) who operate in 30-day development cycles (also called sprints). The Oui development team is a collection of individuals working together to deliver the requested and committed product increments (or iterations). Within the sprint, our development team (see Other Personnel in Budget Justification) will build the Beta [REDACTED]

MILESTONE 2. Completion of Beta [REDACTED] within 30 days.

B.2. Specific Aim 2 – To test the feasibility and acceptability of the beta version of [REDACTED] in a single-group, open-label trial.

B.2.1. Primary Objective. The primary objective of the feasibility portion of the project is to assess the feasibility, and usability of [REDACTED] to deliver targeted CBT to adolescent patients recently hospitalized for SI or suicide attempts. The secondary objectives of this study are to assess the effects on SI and behavior in a

pre/post design of [REDACTED] with adolescent patients being discharged from a hospital.

B.2.2. Endpoints. Consistent with the primary objectives of assessing feasibility, and usability of the intervention, the primary endpoints of this study will be to measure rates and descriptions of recruitment, attrition, data collection, study resources, intervention delivery and acceptability. Hence, our data for this Aim will be descriptive in nature. Formal statistical comparisons will not be performed. Our study will hence focus on process, consistent with a feasibility study. Semi-structured interviews will be conducted by a mental health professional with patients via telephone (according to the Timeline in the Human Subjects and Clinical Trials Information section). Interviews will be recorded digitally for internal use by ADC staff only (e.g., rater training and interrater reliability reviews) and will not be shared with Oui, Therapeutics. Study data will be entered into REDCap. We will use the System Usability Scale (SUS), the Utility of Techniques (UT) questionnaire and also conduct a semi- structured user feedback interview to systematically capture usability and accessibility.

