6 OTHER PLANNED ANALYSES

6.1 OTHER ANALYSES

6.1.1 SYSTEM USABILITY SCALE (SUS)

The SUS is a 10-item instrument used to measure device usability and results in an overall score. Scores will be presented in a table using means, standard deviations, medians, minimums, and maximums over time: at week 4, week 8, and week 12.

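### SAP 1.1.1 leaves suicidal behaviour out of its reading of potential for effectiveness, and the C-SSRS table in 6.1.2 misses two scheduled follow-up assessments and gives no per-participant count of attempts

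*SAP*

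**What the plan says.** The SAP's primary objective (1.1.1) is to "collect descriptive data to support feasibility, acceptability, safety, and potential for effectiveness". Its first bullet then fixes what the last item means: it is to be judged from the "pre-test and post-test scores for SI and depression". Suicidal behaviour is not in that sentence.

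Protocol B.2.1 makes effects a secondary objective and words it more widely: "The secondary objectives of this study are to assess the effects on SI and behavior", in a pre/post design. B.2.5 lists three secondary endpoints to be compared within the group over time: ideation (SIQ), attempts and related behaviours (C-SSRS), and depressive symptoms (PHQ-9).

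The protocol Timeline schedules a lifetime C-SSRS at week 0 and the since-last-contact form at weeks 1, 4, 8, 12 and 16. SAP 1.1.1 lists assessments at baseline and weeks 1, 4, 8 and 12. SAP 6.1.2 presents the C-SSRS by question and construct, as counts and percentages, at weeks 4, 8 and 12. It names neither baseline nor week 1, and nothing in it refers back to the effectiveness bullet.

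**The concern.** The SAP should carry the protocol's effect objective into the analysis. Here one of the two outcomes named in that objective is missing from the sentence that says how effect will be judged, and no reason is given. The omission also matters more in the SAP than it would in the protocol, because the SAP places potential for effectiveness in the primary objective.

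The C-SSRS table in 6.1.2 does not fully make up for this. Since-last-contact data from week 1 are collected under both documents but are not tabulated. Week 16 data are collected under the protocol but fall outside the SAP's visit list altogether. Counts by visit also do not say how many participants had an attempt at any time in follow-up, which is the figure a reader would want next to a fall in ideation or depression. The protocol's Innovation section says that the research to follow this project "would use suicide attempts as a primary outcome", so this pilot's attempt data should be easy to find and complete.

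**Working it through.** The documents state no figure for suicide attempts, so there is none to reproduce. The check compares the texts and then works out what the table can and cannot show.

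**1. Effect outcomes named in each place**

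| Place | Ideation | Suicidal behaviour | Depression |
|---|---|---|---|
| Protocol B.2.1 (effect objective) | yes | yes | no |
| Protocol B.2.5 (secondary endpoints) | yes | yes | yes |
| SAP 1.1.1 (potential for effectiveness) | yes | **no** | yes |

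The SAP keeps two of the three B.2.5 endpoints. The one it omits is named in the B.2.1 objective.

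**2. Visit coverage of the C-SSRS table**

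Inputs: weeks 1, 4, 8, 12 and 16 (protocol Timeline); weeks 4, 8 and 12 (SAP 6.1.2).

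- Assessments tabulated: 3 of 5.
- Nominal windows between assessments: 0–1, 1–4, 4–8, 8–12 and 12–16, that is 1 + 3 + 4 + 4 + 4 = 16 weeks.
- Windows covered by the table: 3 + 4 + 4 = 11 of 16 weeks. Not covered: 1 + 4 = 5 weeks.
- Up to week 12 only, the SAP's own last visit: 11 of 12 weeks. The missing window is the one that ends at the first post-discharge call. The protocol (A.2) stresses the first month after discharge.

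This assumes that every call is completed. If the week 1 call is missed, the week 4 form reaches back over that window.

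**3. From visits to participants**

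Suppose, for illustration, that one participant reports an attempt at each of weeks 4, 8 and 12. The table shows 1, 1, 1. That fits anything from one participant (1/20 = 5%) to three (3/20 = 15%), and the planned output does not say which. Suppose instead that the only attempts are reported by one participant at week 1 and another at week 16. The table shows 0, 0, 0, while the cumulative count is 2/20 = 10%.

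**4. What a cumulative count could show with 20 participants**

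Denominator: 20 (SAP 2; protocol B.2.11). The protocol's 22 to be consented with 10% attrition gives 22 × 0.90 = 19.8, so about 20.

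Exact (Clopper–Pearson) 95% limits for x of n: the lower limit is the 2.5% point of Beta(x, n − x + 1), and the upper limit is the 97.5% point of Beta(x + 1, n − x).

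| Attempters (illustrative) | Percent | Exact 95% interval |
|---|---|---|
| 0/20 | 0% | 0 to 16.8% |
| 1/20 | 5% | 0.1 to 24.9% |
| 2/20 | 10% | 1.2 to 31.7% |
| 4/20 | 20% | 5.7 to 43.7% |
| 10/20 | 50% | 27.2 to 72.8% |

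The intervals for 0/20 and 10/20 do not overlap; those for 0/20 and 4/20 do. The chance of seeing no attempter at all is (1 − p)^20. For assumed true rates p of 5%, 10%, 20% and 30% this is 35.8%, 12.2%, 1.2% and 0.1%. The count is therefore informative only at the extremes.

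**5. Is a pre/post comparison of behaviour possible?**

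Not like for like. The baseline form covers the participant's lifetime and the later forms cover the time since the last contact. The SIQ and PHQ-9 are given at week 0 and again at each follow-up visit.

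**The case against.** The strongest reply is that the SAP had good reason to read effect from the two scales. They repeat at baseline and follow-up, and the C-SSRS forms do not. With one group, no control and about 20 participants, an attempt count says little about effect, and the protocol leaves attempts as an outcome to a later, powered trial. This stands. It limits how the count may be read, but it does not explain why behaviour, which the protocol names in its effect objective, is absent from 1.1.1 without comment.

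The second reply is that behaviour is reported anyway, in 6.1.2 and possibly in the adverse event tables of SAP section 5. This also stands, except for the two assessments missing from 6.1.2 and the missing per-participant total. Adverse event tables by class and term serve the safety objective, which 1.1.1 lists separately.

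A reader might go further in four ways that the documents do not support:

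- *That the protocol makes attempts the standard by which effect must be judged.* Its background section (A.4) says only that "a reasonable marker of lower suicide risk following treatment is a reduction in suicide attempts during the follow-up period". That is one reasonable marker, named in a review of earlier work, and not this study's effect measure.
- *That depression was put in the place of behaviour.* Depressive symptoms are already the third secondary endpoint in B.2.5.
- *That placing the C-SSRS under "6 OTHER PLANNED ANALYSES" demotes it.* The same section holds the SUS, which 1.1.1 uses to determine acceptability. The SAP as supplied has no reporting subsection for the SIQ or PHQ-9 at all.
- *That the study would conclude the same with no attempts or many.* No threshold, test or go/no-go rule returns a verdict. Safety is part of the same objective, and protocol B.2.10 bases the decision on revisions on the data collected, without limiting it to the two scores.

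**Conclusion.** The point holds as a minor misalignment between SAP and protocol. SAP 1.1.1 omits an outcome that the protocol names in its effect objective and lists as an endpoint. The SAP's C-SSRS table takes in 3 of the 5 scheduled follow-up assessments (11 of 16 nominal weeks) and yields no count of participants with any attempt.

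The coverage figures rest on the protocol Timeline being the operative schedule and on completed calls. The protocol's Risk Management paragraph gives a slightly different visit list, without week 12, and the SAP stops at week 12. Within the SAP's own schedule the gap is week 1 alone. The attempt counts used above are illustrative, since the documents give no expected rate. No sample size or planned estimate changes. The loss is in completeness and in how the effectiveness statement is framed.

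**What to change.** 1. Add suicidal behaviour to the effectiveness bullet in SAP 1.1.1, so that it covers ideation, depression and behaviour as protocol B.2.1 and B.2.5 do.
2. Beside the SIQ and PHQ-9 changes, report the number and percentage of participants, with exact 95% intervals, who had (a) any suicide attempt and (b) any other suicidal behaviour. Cumulate over all since-last-contact C-SSRS assessments, including week 1. Give the denominator and the number with complete follow-up.
3. Add week 1 to the visits in SAP 6.1.2. Reconcile the SAP's last visit (week 12) with the protocol's (week 16), and state the window that the count covers.
4. State that with one group of about 20, no control, and a lifetime form at baseline against since-last-contact forms afterwards, the count is descriptive and is not a pre/post estimate of effect.

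The cost is a few lines of SAP text and two rows from data already scheduled for collection. No new assessment or test is needed. The drawback is that the effectiveness statement may read less favourably, and the wide intervals must be shown so that a low count is not taken as evidence of benefit.

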2 SAMPLE SIZE

As proposed in the Phase 1 study, we will enroll 20 participants.

3 GENERAL ISSUES FOR STATISTICAL ANALYSIS

The study will use a frequentist approach to statistical analysis. Descriptive statistics will be used to generate an overall summary of the baseline participant characteristics, and participant disposition. The following summary statistics will be presented unless otherwise stated: Numerical variables will be summarized with sample size, mean, standard deviation, median, minimum, and maximum. Categorical variables will be summarized with frequency and percentages.

4 DEMOGRAPHICS AND OTHER BASELINE CHARACTERISTICS

4.1 DEMOGRAPHICS

All demographics will be summarized, and a listing will be generated, unless otherwise specified. Demographics will include age, gender, race/ethnicity, and sexual orientation,

4.2 CONCOMITANT MEDICATIONS/PSYCHOTHERAPY

All concomitant medications and participation in outpatient psychotherapy will be recorded at the Baseline Visit. The use of ongoing and any new medications will then be noted at each following study visit.

4.3 BASELINE MEDICAL HISTORY

Medical history, the status of each comorbidity (ongoing/resolved), and treatment will be collected by body system (dermatological, cardiovascular, pulmonary, musculoskeletal, abdomen/gastrointestinal, neurological, lymphatic, psychiatric/behavioral, endocrine/metabolic, blood/lymphatic, respiratory, renal, genitourinary, hematological, allergies/drug sensitivities, substance abuse, and other).

5 ADVERSE EVENTS

All adverse events (AEs) will be coded using the standardized Medical Dictionary for Regulatory Activities (MedDRA) central coding dictionary, version 24.1 or greater. AEs will be summarized in the safety population.

5.1 ALL ADVERSE EVENTS

Summaries of incidence rates of individual AEs by System Organ Class (SOC) and Preferred Term (PT) will be prepared. Because a participant may experience more than one AE, summaries will provide both the number of participants experiencing at least one event and the number of events within a reporting period.

5.2 SERIOUS ADVERSE EVENTS

Summaries of incidence rates and relationship to the investigational device of individual SAEs by SOC and PT will be prepared. Summaries will provide both the number of participants and the number of events within a reporting period. Percentages provided will be the percent of participants experiencing one or more serious adverse events.

6 OTHER PLANNED ANALYSES

6.1 OTHER ANALYSES

6.1.1 SYSTEM USABILITY SCALE (SUS)

The SUS is a 10-item instrument used to measure device usability and results in an overall score. Scores will be presented in a table using means, standard deviations, medians, minimums, and maximums over time: at week 4, week 8, and week 12.

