B.2.5. Secondary Endpoints. Diagnostic interviews will be conducted with each participant with the **Mini International Neuropsychiatric Interview Neurocognitive for Children and Adolescents (MINI-KID)**, a widely used, structured diagnostic interview that will be used to verify diagnosis at the screening visit (Sheehan et al 2010). Secondary endpoints will consist of the following measures, assessed using a within-group comparison, over time: **1) Suicidal ideation.** The Suicide Ideation Questionnaire (SIQ) is a 30 – item self or clinician administered instrument used to measure the current intensity of patients' specific distress and suicidal intent, which has been validated for use with adolescents (Pinto et al 1997). Score range is 0-180, with higher score indicating higher intensity. **2) Suicide attempts and other behaviors.** This outcome will be assessed via the Columbia Suicide Severity Rating Scale (CSSRS), which was designed to classify suicide attempts, aborted suicide attempts, and other suicidal behaviors and has been validated for use with adolescents (Gipson et al 2015). **3) Depressive symptoms.** The Patient Health Questionnaire (PHQ-9) is a 9-item self-report form to assess the severity of depressive symptoms that has been widely used in practice and research and validated for use with adolescents. This will be used throughout the study to assess severity of any depressive symptoms each subject is experiencing (Richardson et al 2010).

B.2.6. Participant Remuneration for follow-up sessions. All participants will be paid \$20 for completing each post-discharge assessment (weeks 1, 4, 8, 12, and 16; \$100 total) and a \$25 bonus for completing all assessments. Adolescents and parents/guardians will be paid separately, with separate ClinCards, for their participation (maximum \$125 each). Data from parent/guardians will continue to be collected in cases where participants reach age of maturity during study participation so long as the child continues participation in the study as an adult (i.e., signs adult informed consent form). Parent/guardian date of birth is required in order to register the ClinCards to the parent/guardian. This information will be collected during the consenting process. Payments will not be prorated for partial completion of assessments. Sufficient funding has been budgeted for this portion of the project (see Budget Justification).

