B.2.11. Rationale for Number of Subjects. We will recruit 20 youth age 13-17 years who complete enrollment in the [REDACTED] app. Expecting 10% attrition rate before completing enrollment in the [REDACTED] app we will consent 22 youths to reach our target enrollment number of 20. Means, medians, ranges, and standard deviations for the length of time taken for patients to work through the intervention and for patients to complete the eligibility interview, baseline, post-treatment (8 weeks) and follow-up (12 and 16 weeks) assessments will be reported. In addition, means and SDs will be reported for the length of time it takes project personnel to administer the data collection procedures from invitation through treatment. These data will be used to assess the feasibility of the intervention and study procedures. They will also be used for formal power calculations to design an adequately powered RCT in a subsequent project.

TIMELINE

	Screening Period ^{a, f}	App Testing Period					Follow-Up Period	
Week(W)	W0	W1 ^b	W1-3	W4 ^b	W5-7	W8 ^b	W12 ^b	W16 ^b
Informed Consent	X							
Participant Information Sheet ^c	X							
Medications at Discharge (from medical record)	X							
Medication history form (parent report)		X		X			X	X
Research team phone call with outpatient provider		X						
Enrollment in [REDACTED]	X							
Mini-international neuropsychiatric interview (MINI-KID)	X							

Health Screen Interview	X							
Suicide Ideation Questionnaire (SIQ)	X	X		X		X	X	X
AE Assessment)	X	X		X		X	X	X
Patient Health Questionnaire (PHQ-9)	X	X		X		X	X	X
Columbia Suicide Severity Rating Scale (C-SSRS) - lifetime	X							
Columbia Suicide Severity Rating Scale (C-SSRS) – since last contact		X		X		X	X	X
Frequency of Use of App ^d		X	X	X	X	X	X	X
Interviews for feedback [REDACTED]		X		X		X	X	X
Utility of Techniques		X		X		X	X	X
Usability and Acceptability ^e		X		X		X	X	X
Assessment of healthcare resource utilization (parent report)		X		X		X	X	X

a Screening will be conducted while adolescent patients are at an inpatient psychiatric facility.

b Over the phone with member of the research team

c Sheet to collect demographic and contact information

d Unique logins and duration of each login

e System Usability Scale

f Visit 0 may take place over multiple sessions

RECRUITMENT AND RETENTION PLAN

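### SAP 6.1.1 leaves the week 1 SUS out of its table, so a participant whose only usability score is at week 1 appears in no planned usability summary

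*SAP*

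**What the plan says.** SAP 6.1.1 tabulates the SUS by mean, standard deviation, median, minimum and maximum "over time: at week 4, week 8, and week 12". It gives no reason for choosing those three visits.

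The protocol's Timeline has a row labelled "Usability and Acceptability", and its footnote reads "e System Usability Scale". The row is marked at W1, W4, W8, W12 and W16. Protocol B.2.6 names the same visits when it sets the payments: "post-discharge assessment (weeks 1, 4, 8, 12, and 16".

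SAP 1.1.1 has its own schedule: "Participants will complete assessments at baseline and weeks 1, 4, 8, and 12". Under the same primary objective it says "Acceptability is determined from rates of session completion, rolling retention rate" and, as the third element, the SUS.

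Protocol B.2.1 puts usability in the primary objective, B.2.2 makes both attrition and acceptability primary endpoints, and B.2.3 gives a SUS score of 68 as the lowest sign of a usable system. The SAP states no analysis set for the SUS, no rule for missing scores and no last-available summary. The protocol's paragraph on early withdrawal describes no SUS at exit.

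**The concern.** Week 1 is the only SUS collection before week 4. For someone who takes the week 1 call and is then lost or withdraws, it is the only usability score the trial will hold, and the planned table has no column for it. The table therefore describes people who were still answering at week 4 or later.

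That matters because the SUS is one of three acceptability measures under the SAP's primary objective, and it is the usability questionnaire for which the protocol gives a benchmark. Protocol B.2.10 will use the results to judge whether revisions are needed before a controlled trial. Attrition is itself a primary endpoint, so how leavers rated the app is useful information. If they rated it lower than those who stayed, the tabulated mean would look better than the experience of everyone who gave a score.

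**Working it through.** **Step 1. Set the two schedules side by side.**

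| Visit | Collected (protocol Timeline, B.2.6) | Listed as an assessment in SAP 1.1.1 | Tabulated in SAP 6.1.1 |
|---|---|---|---|
| Week 1 | yes | yes | no |
| Week 4 | yes | yes | yes |
| Week 8 | yes | yes | yes |
| Week 12 | yes | yes | yes |
| Week 16 | yes | no | no |

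Three of five collections are tabulated. The two omissions differ in kind. Week 1 is in the SAP's own schedule, so that schedule does not explain its absence from 6.1.1. Week 16 is absent from the SAP's schedule altogether, so its omission is consistent within the SAP but conflicts with the protocol.

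**Step 2. Who is lost from the SUS summary.**

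- Leaves before the week 1 call: no SUS exists, and adding week 1 does not help.
- Stops using the app but still takes the week 4, 8 or 12 call: can give a SUS and is tabulated.
- Gives a week 1 SUS and none at weeks 4, 8 or 12: the score exists and appears in no planned table. This is the affected group.

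**Step 3. Look for an attrition figure.** Protocol B.2.11 assumes 10% attrition and consents 22 youths to reach 20 (20 × 1.10 = 22; dividing instead gives 20 / 0.90 = 22.2). That allowance covers loss before app enrolment only. No rate is given for loss after enrolment, and no SUS data are given, so the size cannot be derived from the documents.

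**Step 4. Illustrate under stated assumptions.** Let N = 20 be enrolled, all with a week 1 SUS. Let k leave between weeks 1 and 4 with mean L, and let the rest have mean S at week 4. The planned week 4 mean is S. The mean of last scores at that point is ((N − k)S + kL) / N, so the gap is (k/N)(S − L). The values of k, L and S are assumptions.

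- k = 4, L = 50, S = 75: (16 × 75 + 4 × 50) / 20 = 70.0; gap 5.0.
- k = 4, L = 55, S = 72: (16 × 72 + 4 × 55) / 20 = 68.6; gap 3.4.
- k = 2, L = 50, S = 75: (18 × 75 + 2 × 50) / 20 = 72.5; gap 2.5.
- k = 2, L = 55, S = 72: (18 × 72 + 2 × 55) / 20 = 70.3; gap 1.7.

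**Step 5. When would the mean cross 68?** Solve for L with S = 72: L = (68 × 20 − (20 − k) × 72) / k.

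- k = 2: (1360 − 1296) / 2 = 32.
- k = 4: (1360 − 1152) / 4 = 52.
- k = 6: (1360 − 1008) / 6 = 58.7.

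With 2 leavers it would take very low scores to cross the benchmark. With 4 or 6 it would take only moderately low ones.

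**The case against.** The case against giving this much weight is substantial, and most of it stands.

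- **The group is narrow.** The SUS is taken by phone, each assessment is paid, and the retention plan pursues non-responders. A reader might infer that everyone who stops using the app before week 4 drops out of the result. The documents do not support that: app use and answering the call are separate.
- **The direction is not shown.** Nothing in either document says that leavers rate the app lower.
- **The size is assumed.** All four worked examples stay above 68. The protocol describes 68 as a minimal indicator, not a go/no-go rule, and the SAP does not mention it.
- **Early leavers are visible elsewhere.** Session completion, rolling retention and the attrition endpoint can still reflect them, and the feedback interviews and the Utility of Techniques questionnaire are also scheduled at week 1. The loss is specific to the SUS.
- **Week 16 is a different matter.** Quoting 2 of 5 collections (40%) as if all of it concerned early leavers would mix two problems. Only week 1 bears on them.
- **A last-available summary mixes exposures.** At one to two sessions a week, a week 1 score reflects very little of a twelve-session programme.

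These points limit the consequence but do not explain the omission. The SAP schedules a week 1 assessment, the protocol collects the SUS at it, and no reason is given for leaving it out. Limited exposure at week 1 is a reason to label the score by visit, not to leave it unreported.

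**Conclusion.** The mismatch is exact: a SUS score collected at week 1 has no place in SAP 6.1.1, and for a participant with no SUS at weeks 4, 8 or 12 nothing in the planned SUS table replaces it. The table is therefore confined to continuing responders.

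Whether this flatters the result is conditional. It does so only if the missing participants rate the app lower. The gap is then the proportion lost times the difference in means: 3.4 to 5 points with 4 of 20 lost and assumed differences of 17 to 25 points, and 1.7 to 2.5 points with 2 lost. A reader might conclude that the usability result is biased upward or would misstate the comparison with 68. The documents show neither.

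This is a small reporting gap on a measure that serves the primary objective. It is worth closing because the data are already to be collected. Confidence is high in the mismatch and low in any particular size.

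**What to change.** In SAP 6.1.1:

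- Tabulate the SUS at every collected visit, including week 1, and state n at each. Section 3 of the SAP lists sample size among the default statistics, but the list in 6.1.1 omits it, so it should be confirmed.
- Add one descriptive row for the last available SUS of each participant with at least one score, showing how many of those scores come from each visit.

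Separately, reconcile week 16: the protocol follows participants to week 16, while the SAP's assessments end at week 12. The C-SSRS table in SAP 6.1.2 is also limited to weeks 4, 8 and 12 and should be checked at the same time.

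The cost is SAP wording, one or two columns and one row, with no new data and no hypothesis test, so it fits the descriptive design. The drawback is that week 1 scores reflect only early exposure to the app, which is why they should be shown by visit. Splitting the last-available row by app use at week 4 is optional; it would need a definition of use that the documents lack and could leave a cell of very few people.
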